### 7.1.2 Serious Adverse Event (SAE)

A serious adverse event is an undesirable sign, symptom or medical condition which:

- Results in death
- Is life threatening (defined as an event in which the subject was at risk of death at the time of the event; it does not refer to an event which hypothetically might have caused death if it were more severe)
- Requires inpatient hospitalization or causes prolongation of existing hospitalization (see note below for exceptions) for  $\geq 24$  hours
- Results in persistent or significant disability/incapacity
- Is a congenital anomaly/birth defect (note: reports of congenital anomalies/birth defects must also be reported on the Pregnancy Supplemental Form)
- Is an important medical event (defined as a medical event(s) that may not be immediately life-threatening or result in death or hospitalization but, based upon appropriate medical and scientific judgment, may jeopardize the subject or may require intervention [e.g., medical, surgical] to prevent one of the other serious outcomes listed in the definition above.). Examples of such events include, but are not limited to, intensive treatment in an emergency room or at home for allergic bronchospasm; blood dyscrasias or convulsions that do not result in hospitalization.)

Events **not** considered to be serious adverse events are hospitalizations for the:

- Admissions as per protocol for a planned medical/surgical procedure
- Routine health assessment requiring admission for baseline/trending of health status (e.g., routine colonoscopy)
- Medical/surgical admission for purpose other than remedying ill health state and was planned prior to entry into the study. Appropriate documentation is required in these cases
- Admission encountered for another life circumstance that carries no bearing on health status and requires no medical/surgical intervention (e.g., lack of housing, economic inadequacy, care-giver respite, family circumstances, administrative).

The definition of serious adverse event (experience) also includes *important medical event*. Medical and scientific judgment should be exercised in deciding whether expedited reporting is appropriate in other situations, such as important medical events that may not be immediately life-threatening or result in death or hospitalization but may jeopardize the patient or may require intervention to prevent one of the other outcomes listed in the definition above. These should also usually be considered serious.

## 7.2 Relationship

The Principal Investigator must assess whether AEs have a suspected causal relationship to the study drug. A suspected causal relationship is defined as possibly, probably or definitely related:

Definite – The AE is *clearly related* to the study treatment.

Probable – The AE is *likely related* to the study treatment.

Possible – The AE *may be related* to the study treatment.

Unlikely – The AE is *doubtfully related* to the study treatment.

Unrelated – The AE is *clearly NOT related* to the study treatment.

## 7.3 Expectedness

Expected adverse events are those which are expected to occur, according to previous clinical experience, and are listed in the Investigator Brochure. The expectedness of an AE will be assessed by the Principal Investigator:

Unexpected adverse event: An adverse event, which varies in nature, intensity or frequency from information on the investigational drug/agent provided in the Investigator's Brochure, package insert or safety reports. Any adverse event that is not included in the informed consent is considered "unexpected".

Expected (known) adverse event: An adverse event, which has been reported in the Investigator's Brochure. An adverse event is considered "expected", only if it is included in the informed consent document as a risk.

## 7.4 Handling of Expedited Safety Reports

In accordance with local regulations, the IND Sponsor will notify investigators of all SAEs that are unexpected (i.e., not previously described in the IB), and related to the vaccine. This notification will be in the form of an expedited safety report (ESR) that is to be faxed to the investigators and the study coordinators. Upon receiving such notices, the investigator must review and retain the notice with the IB and where required by local regulations, the investigator will submit the ESR to the appropriate IRB. The investigator and IRB will determine if the informed consent requires revision. The investigator should also comply with the IRB procedures for reporting any other safety information.

## 7.5 Reporting Procedures

### 7.5.1 General

All adverse events (both expected and unexpected) will be captured on the appropriate study-specific case report forms (CRFs). In addition, all serious adverse events, regardless of causality to study drug and/or administration device, will be reported promptly to the Sponsor (**[name]**, [REDACTED])

[REDACTED] within 24 hours of recognition of the adverse event (**Appendix D**). If this falls on a weekend or holiday, an email notification is acceptable but must be followed by an SAE reporting form on the next business day. Follow-up information will be submitted to the sponsor as soon as relevant information is available.

### 7.5.2 Institutional Review Board (IRB)

All serious adverse events will be reported to the Institutional Review Board (IRB) per institutional standards. If a serious adverse event requires modification of the study protocol and informed consent, these modifications will be provided to the IRB with the report of the adverse event. Follow-up information will be submitted to the IRB as soon as relevant information is available per institutional standards.

### 7.5.3 Food and Drug Administration (FDA)

#### 7.5.3.1 Expedited IND Safety Reports:

##### *7 Calendar-Day Telephone or Fax Report:*

The Sponsor is required to notify the FDA of any fatal or life-threatening adverse event that is unexpected and assessed by the investigator to be at least possibly related to the investigational agent. Such reports are to be telephoned or faxed [REDACTED] to the FDA within 7 calendar days of first learning of the event.

Follow-up information will be submitted to the FDA as soon as relevant information is available.

##### *15 Calendar-Day Written Report:*

The Sponsor is required to notify the FDA of any serious adverse event that is unexpected and possibly related to the investigational agent in a written IND Safety Report.

Written IND Safety Reports should include an Analysis of Similar Events in accordance with regulation 21 CFR § 312.32. All safety reports previously filed with the IND concerning similar events should be analyzed. The new report should contain comments on the significance of the new event in light of the previous, similar reports.

Written IND safety reports with Analysis of Similar Events are to be submitted to the FDA within 15 calendar days of first learning of the event. Follow-up information will be submitted to the FDA as soon as relevant information is available.

#### 7.5.3.2 IND Annual Reports

In accordance with the regulation 21 CFR § 312.33, the Sponsor shall within 60 days of the anniversary date that the IND went into effect submit a brief report of the adverse events and progress of the investigation. Please refer to Code of Federal Regulations, 21 CFR § 312.33 for a list of the elements required for the annual report. All IND annual reports will be submitted to the FDA by the Sponsor-Investigator.

### 8. PHARMACEUTICAL INFORMATION

*Please refer to the Laboratory Manual for further details regarding storage, preparation, and administration of the product.*

#### 8.1 TA-CIN

**Product Description:** The final formulated product TA-CIN (HPV16 L2E7E6 fusion polypeptide) contains 0.19 mg/mL TA-CIN in 5mM phosphate, 5mM glycine, 0.9mM cysteine at pH8.1 ± 0.3. The product is supplied by the Waisman Biomanufacturing (Madison, WI). The vaccine will be supplied in 0.65mL aliquots.

**Storage Requirements:** Vaccine supply is to be stored at  $\leq -20^{\circ}\text{C}$ .

**Solution Preparation:** Thaw individual vials at ambient temperature. TA-CIN should be removed from  $-20^{\circ}\text{C}$  storage and allowed to defrost at room temperature for up to 30 minutes. **Do not refreeze once defrosted.** Gently invert the vial 5-6 times before dose is drawn up. Using a 25G (orange) or 23G (blue) needle and 1mL syringe, remove 0.53 mL of the clear solution. Administer a total volume of 0.53 mL by intramuscular vaccination within 2 hours of drawing up into the syringe.

**Stability:** Administer a total volume of 0.53 mL by intramuscular vaccination within 2 hours of drawing up into the syringe.

**Route of Administration:** The vaccine will be administered via one of two injection sites: 1) Intramuscular needle injection in the non-dominant medial deltoid (arm) region

using a 25 gauge needle, or 2) Intramuscular needle injection in the Vastus Lateralis (thigh) region using a 23 or 25 gauge needle. In the event that the specified arm or thigh is contraindicated, the other arm or thigh may be used respectively. A patient will receive all 3 injections in the arm if randomized to this group, or all 3 injections in the thigh if randomized to the alternate group.

**Known Adverse Effects:** TA-CIN has been administered in over 90 adults (healthy adults and high grade VIN or AGIN 3 patients) across four clinical trials. To date, no patients with a history of advanced cervical cancer have received the TA-CIN vaccine. Based on the previous clinical safety data for TA-CIN, the following adverse events are expected when administering the TA-CIN vaccine:

System/Organ	Adverse Event	
Blood/Lymphatic	Eosinophilia	
Constitutional	Chills Fatigue Fever	Flu-like symptoms Flushing Somnolence
Dermatologic	Rash	Urticaria
Gastrointestinal	Abdominal Pain Anorexia	Nausea Vomiting
HEENT	Dry Mouth	Rhinitis
Neurology	Dizziness Dreaming Abnormal	Headache Syncope
Vaccine Site Reactions	Bruising Erythema Pain	Pruritis Swelling Tenderness
Other	Arm Weakness Hypotension Menstrual Disorder	Myalgia Pain in both arms

## 9. CORRELATIVE STUDIES

*Please refer to the Laboratory Manual for further details regarding collection, processing and handling of specimens for the correlative studies.*

### 9.1 Blood Samples for Immunologic Assays and Viral DNA

Blood will be drawn at various time schedules as noted in the protocol. The volume of blood and container utilized will vary depending on the test to be performed, as detailed below:

#### 9.1.1 HPV16 L2, E6, E7 and HPV Neutralizing:

Blood (1, 10cc SST [serum separator tube]) will be utilized for measurement of antibodies to HPV16 L2, E6, and E7 via

ELISA per routine laboratory methods and also the HPV in vitro neutralization assay.

- 9.1.2 **HPV16 E6- and E7-Specific T cells:** Blood (1, 60cc heparinized syringe) will be collected to evaluate HPV16 antigen-specific T cell responses at the indicated time points during the vaccination series.
- 9.1.3 **Evaluation of the Proliferative Responses of Peripheral Blood Lymphocytes to Stimulation by HPV16 E6 and E7:** Evaluation of the proliferative responses of peripheral blood lymphocytes to stimulation by HPV16 E6 and E7 using heparinized blood sample (see 9.1.2).
- 9.1.4 **Evaluation of HPV16 DNA in Plasma.** Plasma and cells will be separated from blood (1, 10cc EDTA) by standard protocol and stored at -70 °C until processing. HPV DNA load in plasma samples will be quantified by use of real-time quantitative PCR and T cell receptor sequencing performed.

## 9.2 Samples for HPV16

Tissue will be sent as part of a “pre-screening” consent process for eligibility purposes, as detailed below:

- 9.2.1 **HPV16 *in situ* Hybridization and p16 Immunohistochemistry Testing:** Fresh-frozen or paraffin-embedded material from the cervical cancer tumor specimen must be available for testing to confirm eligibility if this was not done per routine care. Samples will be sent to Johns Hopkins for analysis in a CLIA-certified environment and results will be returned to the study team/provider (**Appendix C**). Sites will be provided with instructions on how to send samples to Johns Hopkins for testing at time of activation.

In the event that standard of care HPV16 testing was done and is positive, and is felt to be adequate by the Protocol Chair, repeat testing will not be needed for eligibility purposes prior to screening and enrollment on the primary treatment study. In these cases archival tissue specimens will still be obtained for research analyses.

## 9.3 Other Assessments

**Disease Status Evaluation:** After completion of standard therapy, disease status will be determined by current standard of care. Disease assessment after vaccine administration is to be performed as per current clinical care standards. Imaging studies, specifically a PET/CT, CT, or MRI scan (whichever is clinically indicated and/or preferred by the treating physician), will be performed per standard of care and/or based on the discretion of the treating physician.

## 10. STUDY CALENDAR

Test/Procedure	Pre-Study 	Week 1 Day 1	Week 2 Day 1	Week 5 Day 1	Week 6 Day 1	Week 9 Day 1	Week 10 Day 1	Week 11-13	Month 6	Month 12	Month 24
Visit Window (Days)	-60		+/- 2	+/- 5	+/- 5	+/- 5	+/- 5		+/- 28	+/- 28	+/- 28
TA-CIN Administration 		X		X		X					
Tumor HPV Testing 	X										
Informed Consent	X										
Demographics	X										
Medical History	X										
Class I and II HLA Typing 	X										
HIV/Hepatitis Panel 	X										
Physical/Pelvic Examination 	X	X		X		X		X	X	X	X
Vital Signs 	X	X		X		X		X	X	X	X
Performance Status 	X	X		X		X		X	X	X	X
Concomitant Med Review	X	X		X		X		X	X	X	X
Vaccine Site Assessment 				X		X		X			
Phone Call			X		X		X				
CBC w/Diff, Plts 	X	X		X		X		X	X	X	X
Serum Chemistry 	X	X		X		X		X	X	X	X
PET/CT, MRI or CT Scan 	X										
Evaluation of HPV16 E6, E7-Specific CD8 + T Cells 	X 			X 		X 		X 	X 	X 	X 
Evaluation of HPV16 Antibody and DNA  and HPV16 Viral Load	X 			X 		X 		X 	X 	X 	X 
Adverse Event Evaluation 											
Archived Tumor Tissue 											

Research samples will be collected at the discretion of the PI based on availability of supplies and safety of patient and staff. In order to minimize the need for research-only in-person visits, telemedicine visits may be substituted for in-person clinical trial visits or portions of clinical trial visits where determined to be appropriate and where determined by the investigator not to increase the participants risks. Prior to initiating telemedicine for study visits the study team will explain to the participant, what a telemedicine visit entails and confirm that the study participant is in agreement and able to proceed with this method. Telemedicine acknowledgement will be obtained in accordance with the Guidance for Use of Telemedicine in Research. In the event telemedicine is not deemed feasible, the study visit will proceed as an in-person visit. Telemedicine visits will be conducted using HIPAA compliant method approved by the Health System and within licensing restrictions.

- 1: Administration site (arm or thigh), as assigned.
- 2: Formalin fixed paraffin embedded tumor sections will be tested for HPV16 DNA/RNA *in situ* hybridization and p16 immunohistochemistry.  
NOTE: This may be done as part of a pre-screening consent process and/or at any time prior to enrollment to the main study. Otherwise, there is no window for HPV16 testing for eligibility. Sites without the capability to conduct HPV16 testing will submit slides from archival tissue to Johns Hopkins
- 3: Peripheral blood will be drawn prior to Week1 Day 1 dosing to undergo HLA typing at study site.
- 4: HIV, Hepatitis C Antibody, and HBsAg. Consent will be obtained for HIV testing.
- 5: Complete physical exam, including pelvic exam, will be completed at baseline (pre-study); focused physical examinations will be conducted thereafter. The Week 1 Day 1 physical examination does not need to be completed if the screening physical examination was performed  $\leq$  7 days prior.
- 6: Including (1) heart rate; (2) respiratory rate; (3) body temperature ( $^{\circ}\text{C}$ ), (4) height (centimeters), and (5) weight (kilograms). Height is only to be obtained once during pretreatment evaluation.
- 7: Eastern Cooperative Oncology Group performance status, 0 to 5.
- 8: Vaccine site reactions include, but are not limited to: erythema, induration, pruritis, tenderness, warmth, blisters, and vaccine site flares. Vaccine site reactions should be followed until resolution.
- 9: Sodium, potassium, bicarbonate, chloride, blood urea nitrogen, serum creatinine, glucose, magnesium, calcium, total bilirubin, direct bilirubin, alkaline phosphatase, alanine aminotransferase, aspartate aminotransferase, albumin, total protein. Labs may be collected up to 3 days prior to dosing.
- 10: CBC with differential including absolute eosinophil count, absolute neutrophils, absolute lymphocytes, and platelets. Labs may be collected up to 3 days prior to dosing.
- 11: PET/CT or CT of the chest/abdomen/pelvis at baseline (within 8 weeks) and as clinically indicated. If a subject cannot have a CT scan (e.g., allergy to contrast dye), a non-contrast enhanced PET/CT scan or MRI should be performed. In the event the patient cannot undergo CT, PET/CT, or MRI, a Chest X-Ray should be performed.
- 12: Patients will undergo phlebotomy for the detection of E6 and E7-specific CD8 $^{+}$  T cells.
- 13: 60 cc of whole blood

- 14: 10cc of blood for serum (antibody assays) and 10cc of blood for plasma (for measurement of HPV16 DNA).
- 15: Adverse events will be evaluated up to 30 days after the last vaccination. Any adverse events related to the vaccine will be followed until resolution or until investigator deems the adverse event as chronic and/or stable. An optional skin biopsy may be performed for any systemic rash or vaccine reaction at the site of administration.
- 16: Attempts to obtain additional archival tumor samples in excess to diagnosis that were collected as part of routine clinical care.
- 17: Pre-Study CBC with differential, platelets and serum chemistry do not need to be repeated in Week 1 if done  $\leq$  7 days prior

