### 4.2 Exclusion Criteria

- 4.2.1 Patients with a diagnosis of immunosuppression or prolonged, active use of immunosuppressive medications such as systemic steroids

- 4.2.2 Patients who have had chemotherapy, radiation, biological cancer therapy, or other investigational agents within 28 days prior to the first dose of study drug
- 4.2.3 Patients who have had surgery within 28 days of dosing of investigational agent, excluding minor procedures (dental work, skin biopsy, etc)
- 4.2.4 Patients with an uncontrolled intercurrent illness including, but not limited to, ongoing or active infection, symptomatic congestive heart failure, unstable angina pectoris, cardiac arrhythmia, or psychiatric illness/social situations that would limit compliance with study requirements
- 4.2.5 Patients who have an active autoimmune disease (e.g., rheumatoid arthritis, systemic lupus erythematosus (SLE), ulcerative colitis, Crohn's Disease, multiple sclerosis (MS), ankylosing spondylitis)
- 4.2.6 Patients being chronically treated with immunosuppressive drugs such as cyclosporin, adrenocorticotrophic hormone (ACTH), or systemic corticosteroids
- 4.2.7 Patients with a recognized immunodeficiency disease including cellular immunodeficiencies, hypogammaglobulinemia or dysgammaglobulinemia; patients who have acquired, hereditary, or congenital immunodeficiencies
- 4.2.8 Women of child-bearing potential (i.e., those who have had fertility-sparing procedures for the management of cervical cancer) will be excluded
- 4.2.9 Patient with active or chronic infection of HIV, HCV, or HBV (tested at baseline; see Study Calendar)
- 4.2.10 Patients with non-healed wounds
- 4.2.11 A history of current or recent concurrent malignancy ( $\leq 5$  years) except basal cell cancer.
- 4.2.12 Inability to understand or unwillingness to sign an informed consent document

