## 12. STATISTICAL CONSIDERATIONS

### 12.1 Study Design and Endpoints

This pilot study is a single dose level assessment of the immunologic response as well as the safety and tolerability of administering TA-CIN vaccine via different sites in patients who have a history of HPV16-related cervical cancer. The primary goal is to determine the most favorable injection site for TA-CIN that exhibits the greater HPV-specific immunogenicity. The secondary goal is to evaluate the safety and tolerability profile of TA-CIN in HPV16 related cervical cancer patients.

The primary endpoint is the immune response rate at the time of the fourth follow-up measurement. The measure of immune response to the regimen will be the antigen-specific T cell response, the simulation index of T cell proliferation, and the titer of the antibody response in peripheral blood. Each patient will have one measurement at baseline and 4 measurements at 4 time points after treatment. For each individual patient, a significant immunologic response is defined as the maximum increase in antigen-specific T cell number or proliferation index after administration of TA-CIN by greater than 1.8 times the standard deviation (SD) of the baseline values, and the increase is at least 2-fold. An increase by 1.8 SD establishes a statistically significant reduction at the two-sided .10 level.

This study will evaluate two different sites, thigh and arm, for TA-CIN vaccine administration.

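### The single baseline immune sample may be drawn up to 60 days before dose 1 with no minimum gap from the end of cancer treatment, so immune recovery before vaccination can count towards the responder rise

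*Combined protocol and SAP*

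**What the plan says.** **Sampling schedule (Section 10).** The row that starts "Visit Window (Days" gives -60 for Pre-Study. The row "Evaluation of HPV16 E6, E7-Specific CD8" and the row for antibody, DNA and viral load are marked at Pre-Study, Week 5, Week 9, Weeks 11-13 and Months 6, 12 and 24. Week 1 Day 1 is blank in both.

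**Footnotes (Section 10).** Footnote 12 says "Patients will undergo phlebotomy for the detection of E6 and E7-specific CD8" T cells, and footnotes 13 and 14 give blood volumes. None sets a tighter window. The safety labs do have one: "Labs may be collected up to 3 days prior to dosing". Footnote 3, which asks for blood before the first dose, covers HLA typing only.

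**Endpoint (Section 12.1).** There is a single baseline: "Each patient will have one measurement at baseline and 4 measurements at 4 time points after treatment". A responder is a patient whose maximum rise in T cell number or proliferation index is "greater than 1.8 times the standard deviation (SD) of the baseline values, and the increase is at least 2-fold".

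**Time since treatment.** Section 4.2 excludes chemotherapy, radiation and similar therapy "within 28 days prior to the first dose of study drug". Section 4.1.2 gives an upper limit of 12 months since definitive treatment and no lower limit.

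**Control and analysis.** Under Section 6.2 both randomised groups receive the vaccine. Section 12.5 has no adjustment of immune response for time since treatment or for the interval from baseline to dose 1.

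**The concern.** A pre/post rise can be credited to the vaccine only if the pre value describes the patient just before vaccination. Here it can be weeks old and can follow closely on treatment that may depress lymphocytes. If antigen-specific T cells are recovering over that time, the recovery becomes part of the responder rise.

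Randomisation does not remove this from the response rate, because both groups are vaccinated and the rise from baseline is the only evidence of induction. Section 12.2 makes misreading easier. It expects prior chemo/radiotherapy to lift response above the 9/25 = 36% seen in patients without such treatment, and recovery would look like that priming. For example, if 20% of non-responders crossed through recovery, 36% would become 0.36 + 0.64 x 0.20 = 48.8% with no added vaccine effect.

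False responders in both groups would also narrow the gap on which the choice of site rests.

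**Working it through.** **1. What the windows permit.** I read -60 as days before Week 1 Day 1. Let g be the days from end of treatment to the sample and d the days from the sample to dose 1. The plan requires g + d of about 28 or more and d of 60 or less, and sets no minimum for g.
- Treatment ends day -29, sample on day -28: g = 1, d = 28. Permitted.
- Treatment ends day -61, sample on day -60: g = 1, d = 60. Permitted.
- Treatment ended 10 months earlier: also permitted, and little affected.

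**2. The plan's own figure (Section 12.2).** With X_A ~ Bin(7, p_A) and X_B ~ Bin(7, p_B), the chance of a correct strict pick is P(X_A > X_B), the sum over x > y of P(X_A = x)P(X_B = y).
- 65% v 45%: 69.3%, with ties 15.8% (plan: about 70%).
- 60% v 45%: 62.1% (plan: about 60%).

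Splitting ties equally gives 77.2% and 71.1%, so the plan's figures do not credit ties.

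**3. Illustration of dilution.** Let f be the fraction of true non-responders falsely called responders through recovery, equal in both groups. The observed rate is p' = p + (1 - p)f. The documents give no value for f; 0 to 30% is an assumed range.

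| f | 65% becomes | 45% becomes | Gap (points) | Strict pick, 65 v 45 | Strict pick, 60 v 45 |
|---|---|---|---|---|---|
| 0 | 65.0% | 45.0% | 20 | 69.3% | 62.1% |
| 10% | 68.5% | 50.5% | 18 | 66.7% | 60.0% |
| 20% | 72.0% | 56.0% | 16 | 64.1% | 57.8% |
| 30% | 75.5% | 61.5% | 14 | 61.3% | 55.6% |

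The 45% group is overstated by 5.5, 11 or 16.5 points. The strict pick at 65 v 45 loses 2.6, 5.2 or 8.0 points.

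**4. How much depends on the date of the baseline.** Assume, again without a source, exponential recovery with doubling time T. The fold rise by day t after dose 1 is 2^((60 + t)/T) from a day -60 baseline and 2^(t/T) from a Day 1 baseline. On the calendar the third follow-up sample is near Week 12 (t = 77) and the fourth is Month 6 (t about 180, timed from the first dose under Section 6.5).

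| T (days) | Week 12: day -60 / Day 1 | Month 6: day -60 / Day 1 |
|---|---|---|
| 60 | 4.87 / 2.43 | 16.0 / 8.0 |
| 90 | 2.87 / 1.81 | 6.4 / 4.0 |
| 120 | 2.21 / 1.56 | 4.0 / 2.8 |
| 180 | 1.69 / 1.35 | 2.5 / 2.0 |

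At Week 12 the baseline date alone decides the 2-fold call for T above 77 and up to 77 + 60 = 137 days. At Month 6 it does so only for T above 180 and up to 180 + 60 = 240 days. Section 12.1 reads the primary endpoint at the fourth follow-up measurement, so under this model much of the recovery would cross 2-fold from either baseline. Growth without a ceiling to Month 6 is a convenience. If recovery levelled off sooner, less of it would come after dose 1.

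**The case against.** The strongest case against is that the harm is assumed, and that moving the sample removes only part of it.

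- **Recovery after dose 1 remains.** This stands. The table in step 3 does not split recovery before dose 1 from recovery after it, so its losses are ceilings on what a later baseline recovers. A reader might infer that the fix restores the full 69.3%; the documents do not support that.
- **No recovery rate is given.** This stands. Nor do the documents say whether T cell counts are normalised to total lymphocytes, and a proliferation index is not a cell count. The 1.8 SD condition is also left out of the illustration.
- **Few patients may be exposed.** Partly stands. Entry runs to 12 months after treatment, chemoradiation is not required, and Sections 4.1 and 4.2 demand at least 500 lymphocytes and exclude immunosuppression. If sampling follows completed treatment, a 60-day-old baseline and dosing at the 28-day limit cannot occur together. A sample the day after treatment, 28 to 60 days before dose 1, is still allowed.
- **The site comparison is randomised.** This stands. A reader might infer that the early baseline biases the choice towards arm or thigh. Recovery falls on both groups alike on average, so it dilutes the contrast without favouring a site. Chance imbalance is possible with 7 per group: if 30% of patients were sampled early (assumed), the groups would differ by two or more such patients with probability 38%.
- **Section 2.1 makes safety primary.** True, but Section 12.1 makes immune response rate the primary endpoint and Section 12.5 picks the site on it.

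**Conclusion.** The point holds as a weakness in the timing of the baseline. The plan allows the only pre-dose immune value to be up to 60 days old and to follow treatment with no minimum gap. Any recovery between that sample and dose 1 is counted in the responder rise, with no unvaccinated group to separate it. The effect is a possible inflation of the response rate in both groups and a slight dilution of the site comparison.

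The size cannot be estimated from the documents. On assumed values of f from 10% to 30%, the strict-pick chance at 65% v 45% falls by 2.6 to 8.0 points, and the fix recovers at most that. A reader might go further and conclude that observed responses will be mainly recovery. The documents do not show this: they give no recovery rate, and only patients sampled soon after chemotherapy or radiation are exposed. The case for change rests on its low cost, not on a demonstrated large bias.

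**What to change.** In the Section 10 calendar, move the baseline research samples (footnotes 13 and 14) from Pre-Study to Week 1 Day 1 before injection, or within 3 days before dosing as for the safety labs. In Section 12.1, define that sample as the baseline. For patients already sampled, report the intervals from end of treatment to baseline and from baseline to dose 1. Reporting the time since treatment for all patients would also help readers judge recovery after dose 1, which the move does not remove.

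Cost: a calendar edit, with the same tubes and total research volume at a visit that already takes place. There are two downsides. A failed sample cannot be repeated once the patient is dosed; the 3-day allowance helps only in part. Patients whose Week 1 safety labs are waived under footnote 17 would need a separate research draw at the dosing visit.
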